9.4.1.3 Pupils

As pupils are aged 7-11 years it is considered inappropriate to ask for written assent. Young children may not fully understand the significance of signing a document or even understand what a signature is. Therefore, we will seek verbal informed assent to collect questionnaire data (OBVQ [25], CHU-9D [26] and HIFAMS [31]) only from those pupils whose parent/carer did not return a 'right to object' form. On the day of data collection, a researcher will verbally inform pupils about the trial including what the trial is about, why they have been asked to participate, what they will be asked to do, how much time it will take and what to do if they become upset. Pupils will be given time to ask questions and it will be made clear that they don't have to participate if they don't want to and they do not need to give a reason. Signs of hesitation or distress will be taken to indicate that the pupil withdraws their assent. For those pupils who do not complete questionnaires, alternative arrangements will be provided to allow them to remain in the data collection environment to avoid embarrassment.

9.4.1.4 KS2 teachers and school KiVa team and coordinator

KS2 teachers will receive an information leaflet which will provide brief information about the trial, what is involved and information on pupil privacy and safety. Teachers will be informed that the school's Headteacher has already provided consent for their school to participate in the trial. Therefore, KS2

teachers will be required to deliver the intervention and associated documentation including TSDQ [27] data. Similarly, school administrators will need to provide school data if the headteacher has provided consent for the school to take part in the trial. Teachers may refuse to consent to provide MBI-ES [30], WEMWS [29] and CBSES [28] questionnaire data.

9.4.2 Consent/assent obtained at 12-Month follow-up

9.4.2.1 Parents/carers

Using the same distribution method as outlined in Section 9.4, parents and carers will receive an information leaflet requesting to provide consent to use additional information about their child to assist with the current trial's evaluation. This will include pupil-level data collected by the Department for Education and held on the NPD. Consent will also be sought to allow researchers to contact parents/carers in the future if there is a request to link children's trial data with other data. Consent will also be sought for parents to provide data about contact with the school about bullying by completing the bespoke Client Service Receipt Inventory (CSRI) [34]. Purposively selected parents and carers will receive an information leaflet about participating in qualitative interviews will also be asked to provide their written consent if they agree to take part. They will be informed that they will be offered a £20 voucher as reimbursement for their time.

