9.4 Informed consent

To protect potential participants' (pupils' and parents') privacy, the school will disseminate information sheets, 'right to object' forms and consent forms to parents/carers on the researchers' behalf. Materials will be distributed using the schools' usual communication system. For instance, some schools will use electronic 'parent mail' and others may use paper newsletters. We will request that school uses alternative methods of contact to inform any parents/carers who do not receive information using normal communication systems. We will also ask the school to display trial information on schoolwide forums e.g. school bulletins to ensure that all parents/carers of KS2 children are informed about the trial and have been provided with an opportunity to complete a 'right to object' form.

Potential participants will be able to keep the information sheet (except for pupils; who will not be provided with a written information sheet) which will provide details of who to contact if they require further information about the research or bullying. The right of the potential participant to refuse to participate without giving reasons will be respected. Just prior to conducting the trial assessments, the researcher will inform all participants that they can withdraw their consent/assent up until the data has been collected and the interviews have been conducted. After this, data will not be able to be withdrawn as it will be pseudonymised.

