9.4.1.2 Parents/carers

Information leaflets will be distributed to parents/carers of children at participating schools. Parents/carers will be informed that they have the 'right to object' to their child's data being collected and will be able to complete and return the 'right to object' form if they do not want their child to complete questionnaires to be used in the trial evaluation.

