Economic evaluation: Intervention costs data (e.g. staff training, supervision & resources) including teacher lesson record books reporting time spent in preparation and lesson delivery will be gathered from teachers. Bullying incidence, CHU-9D [26], and a brief bespoke CSRI [34] relevant to the intervention under assessment will be used. The CRSI [34] will ask for frequency of additional services used by children (e.g. through the school's Special Educational Needs Co-ordinator/ team) and parental consultations with school staff regarding bullying. We will collect this school CSRI information at baseline and follow-up through records schools already hold, providing a pro-forma for schools to extract the relevant data. As part of the request for data linkage, consent will be requested from parents at the follow-up data collection point. At the follow-up parents in both trial arms will also be asked to consent to and complete a CSRI [34] for the 12 months preceding follow-up, which will enquire about children's' use of services such as child and adolescent mental health services, General Practitioner and nurse appointments, and productivity losses for parents to take time off work for these consultations. Additional service use data will be available via the routine data linkage aspect of the project (where parents provide consent for this), supplementing the two methods above. Resource use, using the described multiple data sources, will be costed using national unit costs [39-40]. A fully documented Health Economics Analysis Plan (HEAP) will be written, aligning with the SAP, which will be agreed by the co-applicants before data collection has

been completed. The cost- effectiveness analysis will be reported according to the Consolidated Health Economic Evaluation Reporting Standards (CHEERS).

16 Data Management

In the first instance, researchers will aim to collect data electronically on encrypted tablet devices (one per participant). However, if there are technical issues or similar that inhibit this electronic data capture, paper CRFs will be used. Whichever method of data collection is used at baseline will be used at 12 month follow-up within that school, providing no technical issues arise.

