16.1.1 Paper CRFs

In the instance where electronic data capture of pupil and teacher self-reported measures is not possible e.g. technical difficulties, data will be collected on paper CRFs. Prior to data collection, field workers will write participants' unique PID and another non-unique identifier e.g. initials, on the paper CRF then give the CRF to the corresponding participant. A record of participants' names, PIDs and non-unique identifiers will be kept by the researcher in order to facilitate linkage of Baseline and 12 month follow-up data.

As soon as possible after data collection, research assistants from each hub will check the questionnaires for completeness. The top copy of each completed paper CRF should be couriered from each hub to the CTR for data entry within four weeks of collecting data from all sites recruited by the hub. The remaining

copy is to be retained at the hub. Upon receipt of paper CRFs at the CTR, all data will be entered and transcribed by the trial team using a secure data management system. Data from questionnaires will be stored in pseudonymised form, using PIDs and a non-unique identifier e.g. initials. PIDs, non-unique identifiers and corresponding participant names will be held in separate files and will be stored in secure password protected folders. Refer to the trial data management plan for more details.

Parents/carers will complete a paper CSRI [33] questionnaire and send back to the CTR in an addressed, pre-paid envelop.

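### Opt-in consent for NPD linkage is first sought at 12 months, so which pupils enter the linked absence, exclusion and attainment comparisons can depend on arm

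*Protocol*

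**What the plan says.** **Baseline.** Protocol 9.4.1.2 gives parents an opt-out only: "Parents/carers will be informed that they have the 'right to object' to their child's data being collected". Section 9.4 has schools send the materials on the researchers' behalf, and aims to "ensure that all parents/carers of KS2 children are informed about the trial". No consent for linkage or for the parent CSRI is sought at this stage.

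**Allocation.** Section 14.1 says schools learn their arm after baseline data are in. Table 1 puts randomisation in May-June 2020 and follow-up in April-June 2021. Section 11.3 describes KiVa being introduced to parents, with a launch and a parent's guide.

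**Follow-up.** Section 9.4.2.1, using the same school-run distribution route, says "parents and carers will receive an information leaflet requesting to provide consent to use additional information" about the child. Section 15.3 repeats the timing for linkage: "consent will be requested from parents at the follow-up data collection point". It adds that linked service-use data will exist "where parents provide consent for this". For parent-reported costs it says "At the follow-up parents in both trial arms will also be asked to consent to and complete a CSRI", covering the previous 12 months. Section 16.1.1 describes the return: "Parents/carers will complete a paper CSRI [33] questionnaire and send back to the CTR in an addressed, pre-paid envelop".

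**Use.** Section 5.6.1 takes 12-month absence, exclusions and KS2 attainment from the NPD. Sections 14.6 and 15.1 restrict the main analyses to complete cases.

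**The concern.** Randomisation makes the arms comparable in everyone randomised, or in any subset defined before allocation could influence membership. Here the subset with linked data is defined afterwards, by a decision parents take once the arms have had a year of different experience. A KiVa parent who has attended a launch and read the guide may be more, or less, inclined to agree than a usual-practice parent. The parents who agree may also differ in kind between arms. A difference in linked absence, exclusions or attainment could then reflect who consented as well as what KiVa did.

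At stake are tertiary objective 1 and, in a more limited way, the parent-reported service-use data in the economic evaluation. Analysing consenters in their randomised arms keeps the labels right but does not restore the lost comparability.

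**Working it through.** **1. Order of events.**

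| Step | When | Protocol section |
|---|---|---|
| Right-to-object form to parents | Baseline, Feb-Apr 2020 | 9.4.1.2, Table 1 |
| Randomisation | May-June 2020 | Table 1 |
| Schools told their arm | After baseline data collected | 14.1 |
| KiVa introduced to parents | With the programme | 11.3 |
| First request for linkage and CSRI consent | Apr-Jun 2021 | 9.4.2.1, 15.3, Table 1 |

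Both passages on linkage consent place it at follow-up. The protocol states no expected consent rate, so there is no plan figure to reproduce.

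**2. Possible size, continuous outcome (assumed inputs).** Suppose consent follows a normal selection model with uptake p and correlation ρ between consent propensity and outcome, the same ρ in both arms, and no true effect. Consenters' mean is shifted by ρ × φ(z_p)/p SD, where z_p is the p-quantile of the standard normal distribution and φ its density.

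- p = 0.6: 0.3863/0.6 = 0.644
- p = 0.5: 0.3989/0.5 = 0.798
- p = 0.4: 0.3863/0.4 = 0.966

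| Uptake by arm | Difference in φ(z_p)/p | ρ = 0.2 | ρ = 0.3 |
|---|---|---|---|
| 60% v 40% | 0.322 | 0.064 SD | 0.097 SD |
| 50% v 40% | 0.168 | 0.034 SD | 0.050 SD |

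For scale, use the sample-size inputs in 14.3: 57 schools per arm after one dropout, 111 × 0.9 = 99.9 pupils each, ICC 0.02. The effective number per arm is 57m/[1 + (m − 1) × 0.02], with m = 99.9p. At 50% uptake, m = 49.95 and this is about 1,439, so the SE of a standardised difference is √(2/1,439) ≈ 0.037. The two unequal-uptake cases give about 0.038. The shift is then about 1.7 to 2.6 SE at 60% v 40% and 0.9 to 1.3 SE at 50% v 40%. The ICC of 0.02 was for victimisation; a higher ICC for a linked outcome would lower these ratios.

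**3. Binary outcome (assumed inputs).** An SD shift suits exclusions poorly. If pupils with the event are consented r times as often as those without, the odds among consenters are multiplied by r. The spurious odds ratio, usual practice against KiVa, is r(UP)/r(KiVa), whatever the overall uptake. With an 18% event rate (14.3's victimisation rate, used only as an example):

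- r = 1.2 in both arms: 0.216/(0.216 + 0.82) = 20.9% in each arm, odds ratio 1.00.
- r = 1.2 in usual practice only: 20.9% v 18.0%, odds ratio 1.20.
- r = 1.2 in KiVa only: odds ratio 1/1.2 = 0.83.

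Selection that is equally strong in both arms makes the sample unrepresentative without biasing this comparison. In this model an uptake gap alone does no harm, and equal uptake is no guarantee of safety.

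**4. Leavers.** Section 10.2 puts pupil turnover in England at 6%. If leavers' parents cannot be reached through the old school at 12 months, baseline consent would keep linkable only those who agreed: 0.06 × 0.40 = 2.4% to 0.06 × 0.60 = 3.6% of pupils, at the assumed uptake.

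**The case against.** **Few outcomes are touched.** This stands. The OBVQ, CHU-9D/QALYs, intervention costs, baseline absence and school-held CSRI data do not pass through this consent. The primary cost-effectiveness analysis takes a school perspective with quality of life as its outcome (15.3). A reader might infer that the primary result or the whole economic evaluation is compromised; the protocol does not support that. Section 14.4 does put pupil attendance in the imputation model for missing outcomes, but it does not say whether this means linked 12-month absence, so no effect on the primary-outcome sensitivity analysis can be claimed.

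**Parents may not know the arm.** Partly stands. Section 14.2 does not list parents among those who cannot be blinded, and awareness is documented only for KiVa parents. The mechanism does not need usual-practice parents to know their arm; a year of different experience in the KiVa arm is enough.

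**Earlier consent does not cure the CSRI.** This stands. The form covers the 12 months before follow-up and is posted back voluntarily, so response is after allocation whenever consent is taken.

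**Later consent protects recruitment.** A linkage request at baseline could prompt more objections, against the pupil-recruitment thresholds in 9.3.1 and the 10% allowance in 14.3. The risk is real but unquantified. A separate, plainly optional form limits it, and late consent can still be collected.

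**The SAP and health economics plan may deal with it.** They may describe and adjust for selection, and their handling cannot be judged here. They cannot create a set defined before randomisation, because the protocol fixes when consent is sought.

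**Conclusion.** The point holds for linked absence, exclusions and KS2 attainment: entry to those comparisons is decided after randomisation and can depend on arm. It holds in a weaker form for the supplementary parent-reported cost data, where moving consent helps only in part.

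The illustrative bias is about 0.03 to 0.10 SD. It rests wholly on assumed uptake, an assumed correlation common to both arms, and a normal selection model. The true size and direction are unknown and could be nil. A reader might infer that differential consent will occur, or that 6% of pupils are needlessly lost from linkage. The protocol shows only the structural risk, and the leaver gain is about 2.4% to 3.6% under the same assumed uptake and an England-only turnover figure.

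This is a cheap improvement, confined to tertiary linked outcomes and supplementary parent-cost data.

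**What to change.** 1. Add a separate, clearly optional form for linkage and re-contact consent to the baseline parent mailing, before allocation is disclosed.
2. Define the main linked-data set as pupils whose parents consented at that point. Continue to accept consent at 12 months, but show those pupils separately by arm.
3. For the parent CSRI, take consent in the same form if wanted, which gives a denominator fixed before randomisation. Report return rates by arm, and compare responders with non-responders on baseline OBVQ, CHU-9D and absence. Rates alone are not enough, since equal rates can hide different kinds of responder.
4. If baseline contact has already passed, make the same comparison of linkage consenters with non-consenters by arm, and describe the linked results as conditional on consent given after allocation.

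The cost is an ethics amendment and a longer baseline pack, with no new contact with families. The longer pack may slightly raise right-to-object returns, so these should be watched against the thresholds in 9.3.1.

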9.4.2.2 Pupils

A purposively selected group of pupils will be invited to participate in a focus group. Prior to the focus group, a researcher will verbally inform pupils about trial including what the trial is about, why they have been asked to participate, what they will be asked to do and how much time is will take. Pupils will be given time to ask questions and it will be made clear that they don't have to participate if they don't want to and they do not need to give a reason. As indicated previously, it is not appropriate to seek written informed assent from pupils in this age group. Signs of hesitation or distress will be taken to indicate that the pupil withdraws their assent.

9.4.2.3 School staff

Purposively selected staff from KiVa and UP schools will receive an information leaflet about participating in qualitative interviews. They will also be asked to provide their written consent if they agree to take part.

9.5 Registration and Randomisation

9.5.1 Registration

Once school staff have expressed their interest in participating in the trial, a researcher will confirm the schools' eligibility using a standardised checklist. Once eligibility has been confirmed, Headteachers of eligible schools will be required to complete the Consent Form and Agreement. The school will be given a unique site ID and will be randomised to the intervention or UP arm.

9.5.2 Randomisation

Randomisation will be completed at school-level. Randomisation will be coordinated centrally by the CTR. The sampling frame will be prepared and held by the trial Data Manager. Within each of the four trial areas, schools will be organised into the four strata (based on median Free School Meal (FSM) strata and school size). Each school will be assigned an ID number, after which an independent CTR statistician will randomly allocate schools within each stratum to one of two arms using random block allocations. Further detail on this will be included in the randomisation protocol.

10 Withdrawal & lost to follow-up

10.1 Withdrawal

As it is the school's decision to take part in the trial and the Headteacher will provide their consent, parents will not be able to withdraw their children from receiving the intervention as KiVa will be part of the normal school PSE/PSHE provision. However, schools will have the right to withdraw consent for participation in the trial at any time. Individuals (school staff, pupils, parents/carers) will have the right to withdraw their consent for the collection and use of theirs's or their child's data in any aspect of the trial up until the data is collected. Participants will be informed that once data is collected, it cannot be withdrawn from the trial as all data will be pseudonymised by this stage. Distress or reluctance during pupil data collection will be assumed to indicate that the child wishes to withdraw consent to provide data at that time point. Participants' care from any services will not be affected at any time by declining to participate or withdrawing from the trial.

In all instances, schools and participants who consent and subsequently withdraw should complete a withdrawal form (used in the E-Pats trial; a group-based support intervention for parents with young

children who have learning disabilities) or the withdrawal form should be completed on the participant's behalf by the research assistant at the site based on information provided by the participant. School withdrawal forms should be sent to the sites' contact and then forwarded to the Trial Manager(s) in the CTR. Any queries relating to potential withdrawal of a school or participant should be forwarded to the Trial Manager(s) immediately.

10.2 Lost to follow up

The outcome measurements will be assessed at two time points. Baseline measures will be assessed prior to randomisation of schools into the two trial arms (control and intervention conditions, 58 schools [clusters] in each, see section 14.3, sample size). A second set of measurements will take place 12-months post randomisation as per the baseline protocol. As pupil level follow-up is affected by absence on the day of survey and pupil turnover in schools (estimated turnover for England is 6%), alternative times for data collection will be made for those who are absent to minimise attrition. Schools who complete the trial will have the opportunity to receive a monetary incentive to enhance retention (maximum £308 depending on what data is provided). Schools will also be advised that taking part in the trial may help Ofsted/Estyn inspections – especially in the areas of 'Personal Development' and 'Leadership and Management' (Ofsted), and 'Care, Support and Guidance' and 'Wellbeing and Attitudes to Learning' (Estyn).

11 Trial intervention

The KiVa antibullying programme for pupils aged 7 to 11 years was developed in 2006, by [name] and colleagues at the University of Turku, Finland, funded by the Ministry of Education and Culture. The word KiVa means 'nice' in Finnish and, 'Ki' and 'Va' begin the Finnish words for 'against bullying'. The KiVa programme content and rationale are informed by a Social Architecture Model of Bullying that demonstrates the significant role of bystanders in supporting or standing up against bullying [35]. KiVa is fully manualised (the programme manual includes background information, full implementation instructions, curriculum lesson plans, scripts for addressing highlighted bullying incidents, and forms for dealing with incidents).

11.1 Core curriculum

The core curriculum targets pupils in Years 3 and 4 (unit 1), and Years 5 and 6 (unit 2). Each unit contains ten structured ninety-minute lessons, typically split into two 45- minute lessons, delivered fortnightly throughout the school year. Lessons describe how bullying is affected by bystander behaviours and cover understanding and reflecting on emotions, group interactions processes, the mechanisms and consequences of bullying, group pressure and how to reduce different types of bullying, including cyberbullying, and support fellow pupils. The curriculum aims to create an emotionally and socially supportive setting that encourages pupil engagement via oral presentations, role-play, videos, group work, and whole class activities. KiVa covers over half of the PS(H)E provision in Wales and England. Online games to support learning can be played at home and/or school. Class lessons for all four years of KS2 pupils (aged 7-11 years) will be delivered by KS2 class teachers.

